## 14. Analysis of Exploratory Endpoints

Analysis population: Analysis of exploratory endpoints will be performed using the mITT and PP populations. There are two exploratory endpoints in the study. First, the percent of patients who have household contacts who have developed symptomatic, PCR-confirmed COVID-19 by day 57 will be summarized using counts and percentages for each group. This will be done in the second tier analysis.

## 15. Safety Analysis

Analysis population: Safety population. The safety and tolerability of upamostat will be determined by reported AEs, physical examinations, vital signs, and laboratory tests. Patients who receive any study medication, even a partial dose, or who immediately vomit the study medication are considered evaluable for safety.

As noted above, exacerbation of COVID-19-related signs and symptoms are considered lack of efficacy, rather than adverse events. Hospitalization or death from COVID-19 will be considered in the efficacy rather than safety analyses. These events will be followed similarly to serious adverse events, but not counted in the analyses thereof.

In part A of the study, safety data will be analyzed per the outline in section 7, above, to determine which treatment regimen to carry into part B of the study.

All subjects will be assessed regularly for potential adverse events occurring from the time the subject receives the first dose of the study medication until 56 days after the first dose of study medication. Als collected will include Als which newly started on or after the first dosing of the study drug or an existing condition being worse on or after the first dosing of the study drug.

A treatment-related AE is defined as an AE which is considered to be of suspected relationship to the study drug. Adverse events with missing relationship to study drug other than laboratory data-derived AEs will be assessed as treatment-related.

Study: RHB-107-01 Page 22 of 28

The following summaries will be provided:

- AEs will be summarized as follows, overall and by SOC and PT:
  - All AEs 0
  - All related AEs 0
  - AEs leading to discontinuation of treatment 0
  - AEs with toxicity grade >=3 0
  - 0 Serious AEs
  - **Related Serious AEs** 0
  - AEs that led to death 0
  - 0 AEs leading to dose modification

All AEs will be summarized by maximum toxicity grade, SOC, and PT.

If a subject experiences multiple AEs under the same PT (SOC), then the subject will be counted only once for that PT (SOC). If a subject experiences the same AE more than once with different toxicity grade, the event with the highest grade will be tabulated in "by maximum toxicity grade" tables.

All newly abnormal laboratory findings and those abnormal at baseline which change significantly (i.e., by at least one toxicity grade as defined in the National Cancer Institute Common Terminology Criteria for Adverse Events [NCI CTCAE] v5.0) are considered AEs. Laboratory AEs for which there is no clinical intervention will be abstracted from the laboratory data. Laboratory AEs not listed in the NCI CTCAE v5.0 will be considered as grade 1 (mild) if there is no clinical effect or intervention. Laboratory values outside the normal range for certain parameters will not be considered AEs if they are generally not considered as indicating an abnormality; this includes such parameters as liver enzymes and creatinine which are below the normal range. If there is a clinical sequela or intervention, the laboratory abnormality is to be entered in an adverse event report and graded according to the criteria used for clinical AEs.

No missing data will be imputed for this part of the analysis, nor will formal hypothesis testing be performed. For safety analysis with adverse events, the observation with highest severity within the study day during treatment period will be used.

Subject level listing of AEs, vital signs, and laboratory assessments will be provided.

## 16. Additional Safety Analysis

Analysis population: These additional safety analyses will be done using the Safety population.

Page 23 of 28

Study: RHB-107-01

## 16.1 Clinical Safety Laboratory Tests

Laboratory tests and change from baseline at each time point will be tabulated by treatment groups. No inferential testing will be performed to compare the differences between the treatment groups. This is a second-tier analysis.

#### 16.2 Other Parameters

The results from physical examination will be presented in the subject data listings. Vital signs and physical findings will be shown in listings, but no calculations or study report tables will be generated. Findings on physical examination, including vital signs, which constitute clinically significant changes will be listed as adverse events. This will be done in the second-tier analysis.

Supplemental oxygen and ventilator use will be tabulated by treatment arm and overall population. This is applicable only for hospitalized patients; the relevant information will be obtained from hospital records of these patients. This will be prioritized in the first-tier analysis.

The result of rRT-PCR will be tabulated by positive or negative and, for positives, by viral load at each time point assessed and over time. This will be prioritized in the first-tier analysis.

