Swab at baseline (confirmatory of pre-study test, if a prior swab obtained). At baseline, a rapid PCR or antigen test for diagnosis will be performed on site (if PCR or antigen has not been obtained within 5 days of planned start of treatment), and a quantitative PCR, the same as will be used on other study days, also taken and sent to the central laboratory. Then days 8, 15, 29 and 57. Procedure shown in Appendix 1. The baseline specimen will also be sequenced.

Biochemistry profile to include, at a minimum, albumin, alkaline phosphatase, ALT, AST, bilirubin (total). Bicarbonate, BUN, calcium, chloride, creatinine, glucose, LDH, potassium, sodium, and total protein.

^kTests for serum alpha-1-antitrypsin level and whole blood glucose-6-phosphate dehydrogenase (G6PD) deficiency, both to be taken at the day 57 visit only, are optional and will require a separate consent (C), which should be obtained at the day 43 telemedicine visit.

Adverse events and concomitant medications will be recorded by the patient or caregiver daily (first 4 weeks) or d1, 3 and 5 each week (weeks 5-8) in their diary. These will be reviewed at each home or clinic visit or televisit and entered by study staff in the appropriate eCRF forms.

List of Abbreviations

AE Adverse Event

ALT Alanine Aminotransferase
AST Aspartate Aminotransferase

BL Baseline

BUN Blood urea nitrogen

COVID-19 Coronavirus disease 2019

CBC Complete Blood Count

CC50 Cytotoxic Concentration of 50%

CDC United States Centers for Disease Control

CMH Cochran-Mantel-Haenszel

CRF Case Report Form CRP C-reactive protein

CXR Chest X-ray

DSMB Data Safety Monitoring Board

EC Ethics Committee

EC50 50% Effective (Virus-Inhibitory)

ECG Electrocardiogram

EOS End of Study

EOT End of Treatment

FDA Food and Drug Administration

GCP Good Clinical Practice

G6PD Glucose 6-Phosphate Dehydrogenase

HIPAA Health Insurance Portability and Accountability Act

HR Hazard Ratio

ICH International Council for Harmonisation of Technical Requirements

for Registration of Pharmaceuticals for Human Use

IgG Immunoglobulin G
IgM Immunoglobulin M

INR International Normalized Ratio

IRB Institutional Review Board

K_i Inhibitory Constant

LDH Lactate Dehydrogenase

MedDRA Medical Dictionary for Regulatory Authorities

mITT modified Intent-to-Treat

Upamostat for Treatment of COVID-19 Amendment 4 15 June, 2021

NDA New Drug Application

PA Posterior Anterior

PCR Polymerase Chain Reaction

PP Per Protocol

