5.2 Description of Study Procedures

Most study procedures are standard clinical and clinical laboratory procedures.

SARS-CoV-2 Testing

Two baseline SARS-CoV-2 tests will be obtained at the start of the study: a test performed locally to determine eligibility, and an RT-PCR test run in a central laboratory and which allows quantification.

If the patient has a positive result from a PCR or antigen test performed within 5 days of the planned start of treatment (not just screening day if treatment is to start a day or more after screening), a repeat PCR/antigen assay need not be performed. The results must be on an official laboratory report, not word of mouth or doctor's note. A copy of the outside PCR report must be retained by the site as a source document.

If at screening, the patient has not had a positive PCR or antigen test, a rapid test (PCR or antigen) may be performed at the site to determine eligibility. After consent, a second specimen must be taken for shipment to a central laboratory for quantitative PCR and sequencing.

Once a patient has qualified for the study (positive local test for COVID-19 PCR or antigen, determined by the questionnaire to have sufficient symptomatology, and the patient meets all other inclusion/exclusion criteria), the patient is randomized to treatment and the telemetry devices set up.

- Optimally, the screening, randomization and set-up of devices will all occur the same day in the clinic or ER.
- If all procedures cannot be completed the same day, medication can be provided and devices set up the following day, either by visit of study personnel to the patient's home or a return visit by the patient to the facility.

In the event of discrepant results between the rapid PCR/antigen test and standard PCR, results of the rapid PCR/antigen test will determine eligibility, i.e., a patient will not be declared ineligible if the central laboratory PCR is subsequently found to be negative.

Instructions for obtaining and handling samples for SARS-CoV-2 PCR testing are found in Appendix 1 of the protocol.

Study Medication

Study medication will usually be provided to the patient on the initial day of evaluation. In a situation where final eligibility is not determined prior to the patient's leaving the clinic or on the first day of hospitalization, study medication may be provided after the baseline visit, either by the home health staff member who will be seeing the patient or at a return visit to the facility.

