4.1 Missing Data

In general, no imputation of missing data will be done unless specified in the definition of the endpoints

below. Rules for censoring for time to event endpoints will also be described in detail in the definitions

below. Additional rules for imputation of missing data may be determined during blind review of the data

and documented prior to unblinding.

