## 13. Analysis of Secondary Efficacy Endpoints

Analysis population: Analysis will be performed using the mITT and PP populations.

Analysis will be performed not only of symptom resolution and occurrence of new symptoms in aggregate, but also by individual symptoms assessed by investigators as related to COVID-19. This includes both the symptoms in the questionnaire and additional, less common symptoms which are recorded on the AE reports but attributed to COVID-19.

Items 1, 2, and 4 below are first-tier secondary objectives, to be analyzed initially. Items 3, and 5 are second tier objectives, which may be reported subsequently. Comparison between active treatment and placebo of the following secondary efficacy endpoints will be performed:

- 1) Incidence of hospitalization or death: the primary assessment of this endpoint will be among patients in the high risk group. This has been defined preliminarily above. The group may be redefined and recruitment for part B restricted based on analysis at the end of part A.
  Specific COVID-19 symptoms resulting in hospitalization will be tabulated by SOC, PT and severity. Depending on the number of patients hospitalized, this may be shown either as a table or listing.
  - Specific main COVID-19 symptoms resulting in death will be listed per patient.
- 2) The proportion of patients who are PCR-negative at each time point assessed, days 8, 15, 29 and 57 from the start of treatment (landmark analysis);
- 3) Time to resolution of individual disease-related symptoms present at baseline; COVID-19 symptoms, derived from the symptom questionnaires and those events entered as related to COVID-19 on the AE tables will be summarized as well using MedDRA classification by SOC, PT and severity as new COVID-19 symptoms and those worsening on study by at least one grade
- 4) Development of new disease-related symptoms or pneumonia on study;
- 5) Changes in laboratory markers of disease severity, i.e., oxygen saturation, CRP, lymphocyte count and D-dimer levels, from baseline to time points at which these are measured on study.

The time frame for all endpoints unless otherwise stated is from Day 1 (day of first dose of study medication) through study Day 57. The time to event endpoints will be analyzed using the methods described for the primary endpoint above.

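### SAP 16.2 summarises viral load only among PCR-positive results, so a by-arm reading of load after baseline is not a randomized comparison and can understate, or in some settings reverse, an antiviral effect

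*SAP*

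**What the plan says.** The quantity is measured. Protocol 5.2 provides for "an RT-PCR test run in a central laboratory and which allows quantification" at baseline, and the swab footnote to Protocol Table 1 describes "a quantitative PCR, the same as will be used on other study days, also taken and sent to the central laboratory". Swabs follow on days 8, 15, 29 and 57.

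The only planned use of the quantity is in SAP 16.2, where the result is "tabulated by positive or negative and, for positives, by viral load at each time point assessed and over time". On priority, the SAP adds: "This will be prioritized in the first-tier analysis". The parent section states: "These additional safety analyses will be done using the Safety population".

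The other virological analyses are binary. SAP 13 has "The proportion of patients who are PCR-negative at each time point assessed, days 8, 15, 29 and 57" as a secondary endpoint in the mITT and PP populations, and SAP 2.2 makes it first tier. Protocol 7.4.1 has a supportive recovery definition that uses the first negative swab.

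No section gives a detection limit or a value for a negative result. SAP 4.1 states: "In general, no imputation of missing data will be done unless specified in the definition of the endpoints". Protocol 5.2 also allows a negative central result at baseline: "a patient will not be declared ineligible if the central laboratory PCR is subsequently found to be negative".

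**The concern.** Whether a patient is still positive on day 8 or later depends on treatment. A patient whose virus has cleared drops out of the load table, and if the drug works, more patients drop out of the active arms. The remaining positives then differ between arms by selection, and following load over time follows a shrinking, selected set.

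The direction of the bias matters. Clearance tends to remove low loads, which raises the average among those left. A real antiviral effect therefore looks smaller among positives than it is, and under some patterns of clearance it looks like harm.

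Direct antiviral action is part of the drug's rationale (Protocol 1.2 and 1.3), and part A is the stage at which study parameters and analyses may be revised for part B (Protocol 7.6). A misread first-tier virology table is therefore worth preventing. The plan treats other laboratory data differently: SAP 16.1 tabulates change from baseline by treatment group, while viral load gets no change from baseline and no all-patient summary.

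**Working it through.** **The plan's own figure.** There is none for viral load. All load inputs below are assumptions; only the 20 patients per arm (SAP 5.4) and the 150 v 100 split (Protocol 7.1) come from the documents.

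**Formulas.** Let log10 load be normal with mean μ and SD σ, let the limit be L = 2, and let a = (L − μ)/σ.
- Proportion positive: P = 1 − Φ(a)
- Mean among positives: m = μ + σ·φ(a)/P
- Mean over all patients, negatives set at L: P·m + (1 − P)·L

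**1. Uniform shift** (σ = 1.5, placebo μ = 4, drug μ = 3).
- Placebo: P = 0.909, m = 4.27; all patients 0.909 × 4.27 + 0.091 × 2 = 4.06.
- Drug: P = 0.748, m = 3.64; all patients 0.748 × 3.64 + 0.252 × 2 = 3.23.
- Difference: −0.63 among positives, −0.84 over all patients. The sign is right, but the effect is smaller.
- With σ = 1.8 and placebo means from 3.0 to 4.0, the same 1.0 drop shows as 0.43 to 0.58 among positives and 0.61 to 0.79 over all patients.

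**2. Selective clearance** (σ = 1.8, placebo μ = 4; the drug clears half of the positives whose load would be below 4 and leaves everyone else unchanged).
- Placebo: P = 0.867, m = 4.45; all patients 0.867 × 4.45 + 0.133 × 2 = 4.12.
- Positives below 4 make up 0.867 − 0.500 = 0.367 of patients, with mean 3.10. Those above 4 make up 0.500, with mean 5.44.
- Drug: P = 0.500 + 0.367/2 = 0.683; m = (0.500 × 5.44 + 0.183 × 3.10)/0.683 = 4.81; all patients 0.683 × 4.81 + 0.317 × 2 = 3.92.
- Difference: +0.36 among positives, −0.20 over all patients.

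**3. A constructed example at part A size** (20 per arm).
- Placebo: 8 patients at 6, 8 at 3, 4 negative. Drug: 8 at 5.8, 1 at 3, 11 negative.
- Positives only: (48 + 24)/16 = 4.50 v (46.4 + 3)/9 = 5.49. The drug looks 0.99 worse.
- All patients, negatives at 2: (72 + 8)/20 = 4.00 v (49.4 + 22)/20 = 3.57. The drug is 0.43 better.
- Negatives at 1: 3.80 v 3.02. Negatives at 0: 3.60 v 2.47. The direction holds.

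**4. How often the misleading order would appear with 20 per arm** (40,000 simulated trials).
- Half-and-half mix of means 3 and 6, SD 1, with drug effects on the low and high groups of (1.5, 0), (1.5, 0.3) or (2, 0.5): the drug arm has the higher positives-only mean in 64% to 77% of trials, against 9% to 23% for the all-patient mean.
- Uniform shift of 0.5 or 1.0 (mean 4, SD 1.5): 6% to 21%, against 2% to 15%.

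**5. Power, if load were ever tested** (uniform 0.6 drop, placebo mean 3.5, SD 1.8, correlation with baseline 0.5, two-sided 5%).
- 150 v 100: about 37% positives only, 69% all patients, 79% all patients with baseline adjustment.
- 20 v 20: about 9%, 16% and 20%. Nothing is detectable at part A size, and the SAP plans no test there.

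**The case against.** The sentence in SAP 16.2 names no mean, no contrast and no treatment arm. It can be read as one table with negatives as a category and positives broken down by load. That table accounts for every result, and a drug that clears low-load patients would show a larger negative row. Part A analysis is descriptive (SAP 4.3), and the table sits under additional safety analyses. The randomized virological comparison is the PCR-negative proportion. Protocol 1.3 lists six markers of pharmacologic activity, and viral load is not among them. SAP 4.1 and 5.3 allow further data-handling rules at blinded review.

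Most of this stands, and it limits the importance of the point. It does not remove it. The negative counts show how many cleared, but they cannot correct a load summary of those who remain. If the table is not by arm, no comparative load readout is planned at all. Blinded-review rules concern missing data and imputation; a negative PCR is an observed result and may never come up. Protocol 7.4.2 plans a repeated-measures model for changes in continuous variables, but within a list of secondary endpoints that does not include viral load.

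A reader might infer that baseline load is ignored altogether. That goes too far: baseline is an assessed time point, so load there would be tabulated. What is absent is its use as a reference for change.

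**Conclusion.** The point holds as an inexpensive improvement to a descriptive table. SAP 16.2 restricts load to positives, and no other section supplies an all-patient load summary or a change from central baseline. Under a uniform shift of normally distributed log load, the positives-only difference is attenuated (0.63 against 0.84 in the worked case) but keeps its sign. A reversal needs clearance concentrated in low-load patients. The size rests entirely on the assumed distribution, detection limit and pattern of effect.

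Three stronger readings are not supported:
- That the table will make an effective drug look harmful. It can, but only under the selective pattern.
- That dose selection is at risk. SAP 7 rests it on safety, with efficacy counting only if there is a marked difference between doses and pharmacodynamic parameters not used; no section ties this table to a decision.
- That the trial loses power. The 150 v 100 figures apply only if the wording is carried into the separate part B SAP and load is tested there.

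**What to change.** In SAP 16.2, add a table by arm and visit of log10 viral load, and of change from the central baseline load, for all treated patients with a PCR result at that visit.
- Set negatives at the assay's lower limit, treat them as left-censored, or use a rank summary; state which before unblinding.
- Show the numbers negative and missing in each cell.
- State how a patient with a negative central PCR at baseline is handled in the change from baseline.
- Group by randomized arm. As defined in SAP 6, the mITT and Safety populations contain the same patients, so only the arm assignment can differ.
- Keep the positives-only table, labelled as conditional on positivity.

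If viral load is analysed in the part B SAP, use the all-patient version with baseline log10 load as a covariate.

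The cost is a few lines of SAP text and one table from data already collected. The small downside is that the results depend on the value given to negatives; a censored-data or rank method deals with that.

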## **16.3** Analysis of Concomitant Medication

Prior medications are defined as medications taken within 28 days of the Screening Visit until the start of study drug. In addition, COVID-19 vaccinations are recorded in the concomitant medication listings, regardless of how long prior to study entry the vaccinations were received. Concomitant medications are defined as medications with a start date and time after the start of the Day 1 study drug. Frequency summaries of prior and concomitant medications coded with WHO drug dictionary (version Mar2020) will be provided by treatment group.

At each level of subject summarization, a subject is counted once if the subject reported one or more medications. A listing, including reason for use, duration, frequency and dosage of concomitant and prior medication will be provided.

Only prior COVID-19 vaccination will be a first-tier analysis.

#### 17. Subgroup Analysis

Analysis populations: These analyses will be done using the mITT and PP populations. The primary efficacy endpoint, the first secondary endpoint of death/hospitalization, and other secondary endpoints by subgroups including sex (male/female), BMI ( $\geq$ 30, <30), age, (>65,  $\leq$ 65), presence of additional concerning conditions (none, 1 or more or by specific conditions), whether the patient has received the last primary vaccination at least 14 days prior to study entry, whether patient plan to use an antiviral antibody treatment as assessed at baseline, and study region (US vs non-US).

Study: RHB-107-01 Page 24 of 28

## 18. Change from Analysis Specified in the Corresponding Protocol Version

The use of antipyretics will not be included in the assessment of the primary endpoint of sustained recovery as stated in the protocol. This is noted in the endpoint definition above and additional details of this change are provided in the appendix..

Study: RHB-107-01 Page 25 of 28

Part A Statistical Analysis Plan (Version 2.0)

## 20. Appendix. Changes to analysis plan after approval of version 1.0

#### 20.1 Changes implemented in version 2.0

Changes in version 2.0 were implemented prior to any unblinding of any team members.

